6.7.1 Dose modifications and guidance

Substantial acute toxicities should be managed as medically indicated and with temporary suspension of study, as appropriate. Dose reductions and holds are allowed as clinically indicated by the treating physician and if in line with [Table 9](#) and [Table 10](#). For each patient, a maximum of 2 dose reductions will be allowed as presented in [Table 7](#) and [Table 8](#).

Table 7 AZD1775 BID (Cohorts BID 1 and 2) Dose Level Reductions^a

	AZD1775 STARTING DOSE	AZD1775 -1 DOSE LEVEL
AZD1775 BID regimens	125 mg BID	TBD ^b
	150 mg BID	TBD ^b

a Full details of the AZD1775 BID regimens are provided in [Figure 1](#) and [Figure 2](#).

b If dose reduction required below 150 or 125 mg, this is to be discussed on a case by case basis with Medical monitor

Table 8 AZD1775 QD (Cohorts QD 1.1, 1.2, 2.1, 2.2, 2.3, 3.1, 3.2, 3.3, 4.1, 4.2) Dose Level Reductions^a

	AZD1775 STARTING DOSE	AZD1775 -1 DOSE LEVEL	AZD1775 -2 DOSE LEVEL
AZD1775 QD regimens	200 mg QD	TBD ^b	TBD ^b
	250 mg QD	TBD ^b	TBD ^b
	300 mg QD	250 mg QD ^b	TBD ^b

Table 8 AZD1775 QD (Cohorts QD 1.1, 1.2, 2.1, 2.2, 2.3, 3.1, 3.2, 3.3, 4.1, 4.2) Dose Level Reductions^a

AZD1775 STARTING DOSE	AZD1775 -1 DOSE LEVEL	AZD1775 -2 DOSE LEVEL
400 mg QD	300 mg QD	250 mg QD ^b

a Full details of the AZD1775 QD regimens are provided in [Figure 3](#) and [Figure 4](#).

b If dose reduction required below 250 mg, this is to be discussed on a case by case basis with Medical Monitor

6.7.2 Dose modifications due to haematologic toxicity

Complete blood counts (CBC) will be obtained for all patients at the beginning of each treatment cycle (Day 1). If haematologic toxicity occurs (see [Table 9](#)), treatment should be held and ANC and platelets should be monitored weekly until recovery.

Table 9 Cycle Day 1 Haematologic Dose Modifications

Treatment Day Blood Counts and Toxicity			
ANC		Platelets	Action
≥1000/μL	And	≥75,000/μL	No dose modification or interruption
<1000/μL	Or	<75,000/μL	Delay by 1 week intervals until recovery

If haematologic toxicity parameters do not recover within 21 days, the patient should be removed from the study treatment.

Table 10 Neutropenia, Infection, Febrile Neutropenia Dose Modifications and Management

Any Day	

Grade 3 neutropenic fever (ANC <1000/μL + Temperature \geq101°F [38.5°C]) or neutropenic infection
 
Documented infection with Grade 3 neutropenia (ANC <1000/μL)
 
Grade 4 neutropenia (ANC <500/μL >7 days)
 
Grade 4 thrombocytopenia (platelet count <25,000/μL >7 days)
	
Hold dose until recovery.
 
Then, upon resuming dosing, reduce AZD1775 to the next lower dose level^a.

Grade 4 febrile neutropenia or Grade 4 infection with neutropenia (both defined as septic shock)
 
Thrombocytopenic haemorrhage (gross occult bleeding) associated with a platelet count <50,000/μL
	
Discontinue treatment and follow for disease progression.

a No more than two dose reductions will be allowed for any patient. Patients requiring additional dose modifications due to toxicity will discontinue study treatment.

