- aa An optional Pharmacogenetics (PGx) sample will be obtained if the patient consents. If PGx blood sample is not collected at Cycle 1 Day 1, it can be collected any visit until the last study visit. This sample is **optional** and must be taken from patients who have provided informed consent for genetic sampling and analysis.

- bb The haematology blood samples will be taken **before the patient takes their study medication** on Cycle 1 Day 8 and Cycle 2 Day 8. (On this day the patient should bring the study medication to the clinic and take as instructed by the treating physician).
- cc PK samples will be collected at time of AE possibly related to AZD1775 (unless the last dose of study drug was administered > 1 week prior to the event), when imaging is performed for response assessment and at the end of treatment or progression. PK samples will no longer be required after implementation of CSP Version 5.
- dd Patients discontinuing from AZD1775 in the **absence** of PD should have CT scans performed every 3 months from the last dose of study drug until PD has been assessed by the Investigator or the patient begins a new course of cancer therapy or withdraws from the study. If PD has been assessed, patients will then be followed for survival.
- bb Patients discontinuing from AZD1775 in the **presence** of PD will be followed every 3 months after the last dose of study drug for survival, until the last patient has discontinued study drug. The survival follow-up can be done by a medical record review or telephone call at the Investigator's discretion.
- ff Antiemetics will be taken on the same days of AZD1775 dosing, therefore patients in QD Cohorts 1.2, 2.2, 3.2, and 4.2 will take antiemetics on a 5/2 dosing schedule (days 1-5, 8-12 every 21 day-cycle; no treatment on days 6-7 and 13-21). Patients in QD Cohorts 2.3 and 3.3 will take antiemetics on a 5/2 weekly dosing schedule (days 1-5, 8-12 **and 15-19** every 21-day cycle; no treatment on days 6-7, 13-14, and 20-21)
- gg Patients in QD Cohorts 1.2, 2.2, 3.2, and 4.2 will take AZD1775 on a 5/2 dosing schedule (days 1-5, 8-12 every 21 day-cycle; no treatment on days 6-7 and 13-21). Patients in QD Cohorts 2.3 and 3.3 will take AZD1775 on a 5/2 weekly dosing schedule (days 1-5, 8-12 **and 15-19** every 21-day cycle; no treatment on days 6-7, 13-14, and 20-21). See [Figure 3](#) and [Figure 4](#).

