7.2.2 Dose-limiting toxicity

Dose-limiting toxicities will be evaluated during the first 28 days (5/9 Schedule), or first 21 days (both 5/2 Schedules) of AZD1775 monotherapy treatment. If appropriate the DLT observation period can be extended by up to 2 weeks in case of treatment delay due to study drug-related AE. Toxicity will be graded according to the NCI CTCAE v4.03.

Patients must complete Cycle 1 (i.e. 21 days on either 5/2 schedule) or Cycle 1 and Cycle 2 (i.e. 28 days on the 5/9 schedule) safety evaluations and must receive at least 80% of the planned dose to be considered evaluable. Patients receiving less than 80% of Cycle 1 dose (21 days for the 5/2 schedule) or Cycle 1 and Cycle 2 dose (28 days for the 5/9 Schedule) will be replaced unless they experienced a DLT confirmed by the SRT.

Dose-limiting toxicities are defined as any of the following toxicities not attributable to the disease or disease-related process under investigation, that occur from the first dose of study treatment up to the last day of Cycle 2 (first 28 days) for the 5/9 Schedule, or the last day of Cycle 1 (first 21 days) for the 5/2 Schedule, and that meet at least 1 of the criteria below:

1. Haematologic toxicity \geq Grade 4 for more than 7 days including infection with febrile neutropenia
2. Grade 3 thrombocytopenia associated with Grade ≥ 2 bleeding
3. Haematologic toxicity \geq Grade 4 neutropenia or thrombocytopenia for more than 7 days, or Grade 4 Infection with febrile neutropenia, or Grade 3 neutropenic fever, or Grade 3 thrombocytopenia associated with Grade ≥ 2 bleeding.
4. Non-haematologic toxicity \geq Grade 3
5. Liver function tests (LFTs), Grade ≥ 3 total bilirubin, hepatic transaminase ALT or AST or ALP lasting >48 hours, or any change in liver functions tests consistent with Hy's Law (see [Appendix D](#).)
6. Any other toxicity that is clinically significant and/or unacceptable that does not respond to supportive care, results in a disruption of dosing schedule of more than 7 days, or is judged to be a DLT by the investigator in collaboration with the medical monitor.

A DLT excludes:

- Nausea, vomiting, or diarrhoea that responds to supportive care
- Isolated laboratory change of any grade without clinical sequelae or clinical significance
- Alopecia of any grade

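### Table 10 prints two unequal temperatures for neutropenic fever, and Table 9's title and column heading leave unclear whether its count-based hold applies to mid-cycle dosing restarts

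*Protocol*

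**What the plan says.** **Table 9 (Section 6.7.2).** The title is "Cycle Day 1 Haematologic Dose Modifications" and the sentence introducing it also speaks of Day 1: "Complete blood counts (CBC) will be obtained for all patients at the beginning of each treatment cycle (Day 1". The column heading inside the table is "Treatment Day Blood Counts and Toxicity". If ANC is below 1000/μL or platelets are below 75,000/μL, the action is "Delay by 1 week intervals until recovery", with no dose reduction.

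**Table 10 (same section).** This table applies on any day. Its hold-then-reduce row lists Grade 3 neutropenic fever (ANC below 1000/μL with a temperature of at least 101°F, bracketed as 38.5°C), infection with Grade 3 neutropenia, "Grade 4 neutropenia (ANC <500/μL >7 days" and "Grade 4 thrombocytopenia (platelet count <25,000/μL >7 days". Septic shock, or haemorrhage with platelets below 50,000/μL, leads to discontinuation.

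**Mid-cycle dosing (Section 4, Table 4).** Footnote gg restarts dosing on Day 8 in the 5/2 cohorts (QD 1.2, 2.2, 3.2, 4.2), and on Days 8 and 15 in the 5/2 weekly cohorts (QD 2.3, 3.3). The table schedules haematology on Days 8 and 15, and footnote f wants counts reviewed before dosing. Footnote bb, on the Day 8 samples of Cycles 1 and 2, gives no count threshold: "On this day the patient should bring the study medication to the clinic and take as instructed by the treating physician".

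**Physician latitude.** Section 6.7 lets the treating physician hold or reduce on clinical grounds. Section 6.7.1 repeats this, with the condition that the action fits Tables 9 and 10.

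**DLT definition (Section 7.2.2).** Criterion 3 includes "or Grade 3 neutropenic fever" without giving a temperature. The section grades toxicity by CTCAE v4.03.

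**The concern.** There are two separate faults, each inside a single table.

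Table 10 attaches a mandatory hold and dose reduction to a temperature, then prints two values that are not equivalent. Sites that read thermometers in Celsius and in Fahrenheit would treat the same patient differently. A reduction is not trivial, because Section 6.7 allows a patient only two.

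Table 9's title and heading point to different sets of days. On the 5/9 and BID schedules this is harmless: dosing covers Days 1-5 of a 14-day cycle, so every dosing block starts on a Day 1. On the 5/2 and 5/2 weekly schedules a new five-day block starts mid-cycle with a fresh count in hand, and the reader cannot tell whether Table 9's thresholds govern that count.

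What is at stake is consistent dosing across sites and, through doses received, the requirement in Section 7.2.2 that a patient without a DLT receive at least 80% of planned dose to be evaluable.

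**Working it through.** **1. Temperature (Table 10).**
- °C = (°F − 32) × 5/9, so 101°F = (101 − 32) × 5/9 = 38.33°C. The printed 38.5°C is not reproduced.
- °F = °C × 9/5 + 32, so 38.5°C = 101.3°F.
- Gap: 38.5 − 38.33 = 0.17°C, or 101.3 − 101 = 0.3°F.

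| Reading, ANC <1000/μL, no documented infection | 101°F rule | 38.5°C rule |
|---|---|---|
| 38.3°C (100.9°F) | not met | not met |
| 38.4°C (101.1°F) | hold and reduce | not met |
| 38.5°C (101.3°F) | hold and reduce | hold and reduce |

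The band runs from 38.33 to below 38.5°C. A patient in it who is judged by the Celsius figure is held without reduction if Table 9 governs that day; otherwise neither table requires action. A documented infection with ANC below 1000/μL triggers Table 10 at any temperature, so the band matters only without one.

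**2. Scope of Table 9.** Inputs are the dosing days in Table 4 footnote gg and the thresholds in Tables 9 and 10.
- 5/2 schedule: blocks start on Days 1 and 8. A Day 1-only rule leaves 1 of 2 starts without a count threshold.
- 5/2 weekly schedule: blocks start on Days 1, 8 and 15. A Day 1-only rule leaves 2 of 3 without one.
- Affected: 4 + 2 = 6 of the 10 QD cohorts for Day 8, and 2 (QD 2.3 and 3.3) for Day 15.

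Counts found on Day 8 or 15, without fever, infection or bleeding:

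| Count | Table 9 on every treatment day | Table 9 on Day 1 only | Table 10 |
|---|---|---|---|
| ANC 900/μL | hold | silent | not triggered |
| ANC 400/μL for 3 days | hold | silent | not triggered |
| Platelets 60,000/μL | hold | silent | not triggered |
| Platelets 20,000/μL for 3 days | hold | silent | not triggered |
| ANC 400/μL for 8 days | hold | silent | hold and reduce |

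In the first four rows the reading of Table 9 decides whether any written threshold applies. In the last row Table 10 settles the action either way.

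**3. Link to evaluability.** If one five-day block is omitted and not given later, a patient on 5/2 receives 5/10 = 50% of planned doses and a patient on 5/2 weekly 10/15 = 67%. Both are below 80%, so without a DLT the patient is replaced. If the block is given, this shortfall does not arise. Section 7.2.2 allows the DLT window to be extended by up to 2 weeks for a drug-related delay, which can recover some of these patients.

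**The case against.** The best defence of Table 9 is that its title and lead-in sentence both say Day 1, that Day 1 is itself a treatment day, and that the heading can be read under the title. Mid-cycle dosing is then deliberately left to a physician who has a pre-dose count, and Section 6.7 permits clinically indicated holds on any day. This is a workable reading, and a fixed mid-cycle threshold is a design choice. What remains is that the heading supports the other reading equally well, and that Section 6.7.1 ties holds to Tables 9 and 10 without saying what fits them on Day 8. Nothing in this defence answers the temperature mismatch.

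Three stronger readings are tempting but not supported.
- **That Tables 9 and 10 contradict each other.** They can be applied together: Table 9 is a re-treatment threshold and Table 10 a rule for more severe events. Where both apply, both hold, and Table 10 adds the reduction.
- **That Table 10 requires dosing to continue at, say, ANC 400/μL until 7 days have passed.** Its more-than-7-day entries trigger a mandatory action; they do not order dosing before that, and Section 6.7 allows an earlier hold.
- **That the temperature mismatch decides DLTs and hence escalation.** Criterion 3 uses the same term as Table 10, but Section 7.2.2 grades by CTCAE v4.03 and does not cite Table 10's temperature. The link is an inference.

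The titles of Tables 3 and 4 also mark the QD schedules as closed to enrolment, and Section 6.8 has the safety review team take dose interruptions and reductions into account. A change now would do little for cohort DLT rates.

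**Conclusion.** Both faults are real, and the point is minor to moderate.

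The temperature fault is certain and narrow. One mandatory hold-and-reduce rule has two thresholds 0.17°C (0.3°F) apart, and it affects patients with ANC below 1000/μL, no documented infection and a reading between them.

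The Table 9 fault is an ambiguity of scope. It concerns mid-cycle restarts in six QD cohorts, with Day 15 relevant only to QD 2.3 and 3.3. If the title governs, there is a gap filled by physician judgement for any count short of a Table 10 event. If the heading governs, a numeric hold applies. The document does not say which.

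An effect on evaluability is possible by the arithmetic above, but its frequency cannot be estimated from the protocol. It depends on how often such counts occur on Days 8 and 15 and on how sites read the table. The rules still matter for patients on treatment: Section 4.3.2.3 lets them continue beyond the Final Protocol Visit and expects dose changes generally to follow this protocol's approach.

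**What to change.** - **Table 10:** print one temperature, either 101°F [38.3°C] or 101.3°F [38.5°C].
- **Table 9:** make the title and column heading agree by stating whether the hold applies on Day 1 only or at every dosing-week start (Days 1, 8 and 15, as the schedule requires). Which one is for the sponsor to decide.
- **Table 4, footnote bb:** point to Table 9 for the rule on Day 8. If Table 9 is limited to Day 1, state there that dosing on Days 8 and 15 is by physician judgement short of the Table 10 events.

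The cost is a wording change to two tables and one footnote. No new assessment is needed, because the Day 8 and Day 15 counts are already scheduled. For data already collected, the study report should say which reading of Table 9 and which temperature the sites applied.

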6.7.3 Non-haematologic toxicity dose modifications

Substantial acute toxicities should be managed as medically indicated and with temporary suspension of investigational product, as appropriate. Dose reductions or holds and initiation of supportive care are allowed as clinically indicated by the treating physician.

Dose reductions of AZD1775 should be considered if the toxicity is considered to be related to AZD1775. Dose re-escalation is not permitted.

In general, if a patient experiences a G1/G2 non-haematological toxicity, no dose modification is required (except QTc prolongation, see table below). If a patient experiences a G3 or G4 toxicity which is not attributable to the disease or disease-related processes under investigation, dosing will be interrupted and/or the dose reduced, and supportive therapy administered as required. Any patient who develops a Grade 3 or 4 non-haematologic toxicity that does not resolve to \leq Grade 1 within 21 days should be removed from the study treatment unless approved by the Medical Monitor.

Table 11 AZD1775 dose modifications for QTc interval prolongation

Electrocardiogram QT corrected interval prolonged	
QTc Value	AZD1775

Table 11 AZD1775 dose modifications for QTc interval prolongation

Electrocardiogram QT corrected interval prolonged	
QTc 450-480 ms (males) or 470-480 ms (females)	Hold. Once QTc interval has returned to pretreatment status and correction of possible electrolyte imbalance has been made, resume at next lower dose level.
QTc 481-500 ms	Hold. Seek cardiologist advice, patient may resume at next lower dose level if cardiologist agrees.
QTc \geq 501 ms	Discontinue treatment. Seek cardiologist advice.
Shift from baseline of \geq 60ms	Discontinue treatment. Seek cardiologist advice.

6.7.4 Non-haematologic toxicity management guidelines

6.7.4.1 Diarrhoea

Due to frequent reports of diarrhoea with AZD1775 administration, vigorous anti-diarrhoeal treatment loperamide (Imodium) is required at the **first** onset of diarrhoea according to American Society of Clinical Oncology (ASCO) guidelines. Oral loperamide (Imodium) 4mg should be administered at the first onset of diarrhoea and then 2mg every 2 hours until diarrhoea-free for at least 12 hours. The first dose of loperamide could be lowered to 2mg if the diarrhoea is recurrent and if, in the opinion of the treating physician, the diarrhoea is not severe.

Patients should be instructed to notify the Investigator or research staff for the occurrence of blood or black stools, symptoms of dehydration, fever, inability to take liquids by mouth, and inability to control diarrhoea within 24 hours of using loperamide or other prescribed anti-diarrhoeal medications.

If diarrhoea is severe (i.e., requiring IV rehydration) and/or associated with fever or severe neutropenia (Grade 3 or 4), broad-spectrum antibiotics must be prescribed. Patients with severe diarrhoea or any diarrhoea associated with severe nausea or vomiting should be hospitalized for IV hydration and correction of electrolyte imbalances.

6.7.4.2 Nausea and vomiting (mandatory antiemetic prophylaxis)

For patients on BID dosing, all patients must receive a 5-HT₃ antagonist, ondansetron (Zofran) 8 mg PO BID or granisetron (Kytril) 1 mg PO BID prior to each dose of AZD1775. Additional doses of 5-HT₃ antagonist may be used if needed. In addition, dexamethasone 4 mg PO will be given with each AZD1775 dose as a minimum on the first day of dosing AZD1775 of every 3-5 days dosing period, unless contraindicated or not well-tolerated. Dexamethasone may be continued on further days of dosing, potentially at a lower dose. Dexamethasone or the 5-HT₃ antagonist may be given by IV as needed.

For patients on QD dosing, all patients must receive a 5-HT₃ antagonist, ondansetron (Zofran) 8 mg PO QD or granisetron (Kytril) 1 mg PO QD prior to each dose of AZD1775. If nausea and vomiting continue, a second dose of antiemetics can be taken 8 hours later if necessary. In addition, dexamethasone 4 mg PO will be given with each AZD1775 dose unless contraindicated or not well-tolerated. Dexamethasone or the 5-HT₃ antagonist may be given by IV as needed.

Promethazine (Phenergan), prochlorperazine (Compazine), and benzodiazepine may still be used as additional adjunctive treatments during AZD1775 therapy.

Please note: aprepitant [Emend] and fosaprepitant are not permitted due to known DDIs.

Patients should be strongly encouraged to maintain liberal oral fluid intake.

Suitable alternative medications may be used, with adequate justification, in those studies where the use of any of the above medications might interfere with other study procedures or are deemed insufficient.

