- s All patients will be followed during the off-treatment period until all treatment related toxicity resolves, or for at least 30 days post-study drug discontinuation or until new therapy. This can be done via telephone contact at the Investigator's discretion. All concomitant medications received 30 days after the last dose of study medication(s) should be recorded in the medical record and eCRF.
- t AZD1775 PO BID, over 5 days (10 doses), on Days 1-5 every 14 days. Fasting is required on Cycle 1 Day 1 for the food effect assessment portion of this study.
- u All patients must receive a 5-HT3 antagonist, ondansetron (Zofran) 8 mg PO BID or granisetron (Kytril) 1 mg PO BID prior to each dose of AZD1775. Additional doses of 5-HT3 antagonist may be used if needed. In addition, dexamethasone 4 mg PO will be given with each AZD1775 dose as a minimum on the first day dosing AZD1775 of every 3-5 days dosing period, unless contraindicated or not well-tolerated. Dexamethasone or the 5-HT3 antagonist may be given by IV as needed. Please note: aprepitant [Emed] and fosaprepitant are not permitted due to known drug-drug interactions (see Section 6.7.4.2).
- v Due to frequent reports of diarrhoea with AZD1775 administration, vigorous anti-diarrhoeal treatment loperamide (Imodium) is required at the first onset of diarrhoea according to ASCO guidelines. Patients should be instructed to take oral loperamide (Imodium) 2 mg every 2 hours until diarrhoea-free for at least 12 hours.
- w When applicable, tumour markers that are elevated and are used by the investigator to monitor for tumour response will be collected at baseline, Day 1 of each cycle and at the end of treatment. The tumour marker analysis will be performed by a local laboratory.
- x Previous individual patient genomic profile reports should be provided for this study.

- y An optional Pharmacogenetics (PGx) sample will be obtained if the patient consents. If PGx blood sample is not collected at Cycle 1 Day 1, it can be collected any visit until the last study visit. This sample is **optional** and must be taken from patients who have provided informed consent for genetic sampling and analysis.

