- w All patients must receive a 5-HT₃ antagonist, ondansetron (Zofran) 8 mg PO QD or granisetron (Kytril) 1 mg PO QD prior to each dose of AZD1775. If nausea and vomiting continue, a second dose of antiemetics can be taken 8 hours later, if necessary. In addition, dexamethasone 4 mg PO will be given with each AZD1775 dose as a minimum on the first day dosing AZD1775 of every 3-5 days dosing period, unless contraindicated or not well-tolerated. Dexamethasone or the 5-HT₃ antagonist may be given by IV as needed. Please note: aprepitant [Emend] and fosaprepitant are not permitted due to known drug-drug interactions (see Section 6.7.4.2).
- x Due to frequent reports of diarrhoea with AZD1775 administration, vigorous anti-diarrhoeal treatment loperamide (Imodium) is required at the first onset of diarrhoea according to ASCO guidelines. Patients should be instructed to take oral loperamide (Imodium) 2 mg every 2 hours until diarrhoea-free for at least 12 hours.
- y When applicable, tumour markers that are elevated and are used by the Investigator to monitor for tumour response will be collected at baseline, Day 1 of each cycle, at the end of treatment and FPV. The tumour marker analysis will be performed by a local laboratory.
- z Previous individual patient genomic profile reports should be provided for this study.
- aa An optional Pharmacogenetics (PGx) sample will be obtained if the patient consents. If PGx blood sample is not collected at Cycle 1 Day 1, it can be collected any visit until the last study visit. This sample is **optional** and must be taken from patients who have provided informed consent for genetic sampling and analysis.

- bb PK samples will be collected at time of AE possibly related to AZD1775 (unless the last dose of study drug was administered > 1 week prior to the event), when imaging is performed for response assessment and at the end of treatment or progression. PK samples will no longer be required after implementation of CSP Version 5.
- cc Patients discontinuing from AZD1775 in the **absence** of PD should have CT scans performed every 3 months from the last dose of study drug until PD has been assessed by the Investigator or the patient begins a new course of cancer therapy or withdraws from the study. If PD has been assessed, patients will then be followed for survival.

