7.8 Concomitant and other treatments

7.8.1 Permitted concomitant medications

All concomitant medications received within 14 days before the first dose of study medication and 30 days after the last dose of study medication should be recorded. Concomitant medications must be recorded in the appropriate sections of the eCRF.

Supportive Medication/Class of drug:	Usage:
Anti-emetics (excluding aprepitant [Emend] and fosaprepitant)	Premedication with anti-emetics is mandatory (excluding aprepitant [Emend] and fosaprepitant) as presented in Section 6.7.4.2
Loperamide (Imodium)	Loperamide (Imodium) is required at the first onset of diarrhoea according to ASCO guidelines (see Section 6.7.4.1).
Medications including but not limited to the following: 
 • Bisphosphonates and receptor activator of nuclear factor kappa-B ligand (RANKL) inhibitors (e.g. denosumab). • Patients requiring therapeutic warfarin or coumadin-derivative anticoagulants will be monitored with INR and Prothrombin Time (PT) as clinically indicated. • Low molecular weight heparin, rivaroxaban, or equivalent anticoagulant therapy is permitted where clinically indicated. • Patients may receive treatment with megestrol acetate when prescribed for appetite stimulation. 	Medications may be administered for maintenance of existing conditions prior to study enrolment or for a new condition that develops while on study.

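### Study-plan footnotes leave out the 4 mg first loperamide dose and give once-daily patients a first-day dexamethasone minimum that Section 6.7.4.2 states only for twice-daily patients

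*Protocol*

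**What the plan says.** **Loperamide.** Section 6.7.4.1 states: "Oral loperamide (Imodium) 4mg should be administered at the first onset of diarrhoea and then 2mg every 2 hours until diarrhoea-free". It allows one exception: "The first dose of loperamide could be lowered to 2mg if the diarrhoea is recurrent", and then only if the treating physician judges the diarrhoea not severe. Footnote v of Table 2 (BID) and footnote x of Tables 3 (QD 5/9) and 4 (QD 5/2 schedules) also require loperamide from the first onset of diarrhoea, but the dose they give is different: "Patients should be instructed to take oral loperamide (Imodium) 2 mg every 2 hours until diarrhoea-free for at least 12 hours".

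**Dexamethasone.** Section 6.7.4.2 has one paragraph for each regimen. For BID patients, 4 mg is given "as a minimum on the first day of dosing AZD1775 of every 3-5 days dosing period", and continuing on later days is optional. For QD patients the instruction is: "In addition, dexamethasone 4 mg PO will be given with each AZD1775 dose unless contraindicated or not well-tolerated". Footnote w of Tables 3 and 4, which cover QD patients only, reads "as a minimum on the first day dosing AZD1775 of every 3-5 days dosing period" and ends with a cross-reference to Section 6.7.4.2.

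**Which text governs.** Section 7.8.1 says "Premedication with anti-emetics is mandatory (excluding aprepitant [Emend] and fosaprepitant) as presented in Section 6.7.4.2", and for loperamide it points to Section 6.7.4.1.

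**The concern.** The study-plan tables are what site staff work from at each visit, and the loperamide footnotes say what patients are to be told. Patients take study drug at home, so that instruction is the one they would follow when diarrhoea starts. A site working from the tables could tell a patient with a first episode to start at 2 mg when the body text says 4 mg. It could also give a QD patient dexamethasone on the first day of a dosing block only, when the body text asks for it with every dose. Each text reads as complete, so someone holding only one of them has no reason to suspect a difference. At stake is consistent supportive care for patients receiving the drug.

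**Working it through.** The protocol states no figure to reproduce here. The check sets the texts side by side.

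| Item | Body text | Study-plan footnote | Same? |
|---|---|---|---|
| Loperamide, first dose of a first episode | 4 mg (6.7.4.1) | 2 mg (Table 2 v; Tables 3 and 4 x) | No |
| Loperamide, later doses | 2 mg every 2 hours (6.7.4.1) | 2 mg every 2 hours | Yes |
| Loperamide, recurrent and non-severe | first dose may be 2 mg (6.7.4.1) | 2 mg | Compatible |
| Dexamethasone, BID | first day of each dosing period as a minimum (6.7.4.2) | same minimum (Table 2 u) | Yes |
| Dexamethasone, QD | with each AZD1775 dose (6.7.4.2) | first day of each dosing period as a minimum (Tables 3 and 4 w) | No |
| 5-HT3 antagonist, QD | before each dose, with a second antiemetic dose 8 hours later if needed (6.7.4.2) | same (Tables 3 and 4 w) | Yes |

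1. **Loperamide.** The difference is 4 mg − 2 mg = 2 mg, in the first dose only. The exception in Section 6.7.4.1 does not reconcile the texts. It is limited to recurrent diarrhoea that is not severe, while the footnotes apply from the first onset.

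2. **Dexamethasone, meaning of the footnote.** Footnote w is awkwardly worded, because it mentions each dose and then a first-day minimum. The BID paragraph of Section 6.7.4.2 uses nearly the same phrase and adds that later days are optional. The phrase therefore sets a floor.

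3. **Dexamethasone, comparison.** In a five-day QD dosing block, Section 6.7.4.2 requires dexamethasone on 5 days (absent contraindication or intolerance) and footnote w requires it on 1. Dosing on all 5 days meets both texts. Dosing on day 1 alone meets footnote w but not the QD paragraph.

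4. **Status of the text.** Both differences are in the current Version 5 body and tables. Neither depends on the summary of changes.

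**The case against.** The strongest reply is that the footnotes are abbreviations and the governing text is easy to find. Footnote w cites Section 6.7.4.2, and Section 7.8.1 points to Sections 6.7.4.1 and 6.7.4.2. That stands, and it settles the direction of the correction. It does not remove the mismatch. The loperamide footnotes do not cite Section 6.7.4.1, and both sets of footnotes state a specific rule that differs from the section.

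A second reply is that little use is left for these tables. All three are marked closed to enrolment, and under Section 4.3.2.3 care after the Final Protocol Visit follows local practice. That also stands and keeps the point minor.

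Three stronger readings are tempting, and the documents do not support them.

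- **Table 4 contradicts itself.** Footnote ff says "Antiemetics will be taken on the same days of AZD1775 dosing", and a reader might set this against footnote w. But dosing on every day satisfies a minimum. Footnote ff also does not name dexamethasone, so the 5-HT3 antagonist before each dose may be all it means.
- **The mismatch shifts DLT classification.** Section 7.2.2 excludes nausea, vomiting or diarrhoea that responds to supportive care, so a reader might infer an effect on the primary outcome. The exclusion turns on whether the event responds, not on which prophylaxis came first. A patient at the footnote floor may still receive a second antiemetic dose, IV dexamethasone or 5-HT3 antagonist, promethazine, prochlorperazine or a benzodiazepine. Severe diarrhoea leads to hospital care. DLTs go to the Medical Monitor, and the Safety Review Team reviews each cohort.
- **The gap is large over the DLT window.** On the 5/9 schedule, two cycles give 2 × 5 = 10 dosing days, against a floor of 2. That is a worst case for a closed cohort, and nothing in the protocol shows that any site dosed at the floor. It describes the wording and is not evidence of impact.

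**Conclusion.** The point holds as a minor internal inconsistency in operative supportive-care instructions. The loperamide mismatch is the clearer of the two: the footnotes give half the first dose that Section 6.7.4.1 states for a first episode, a one-time 2 mg gap. The dexamethasone mismatch is between footnote w and the QD paragraph of Section 6.7.4.2. It matters only where a site gives the minimum and no more.

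Two assumptions are made. The first is that the first-day phrase means a floor in footnote w, as it does in the BID paragraph. The second is that Sections 6.7.4.1 and 6.7.4.2 govern, because Section 7.8.1 points to them. The remaining effect is limited to the care of patients still on treatment. No sample size, error rate, DLT definition or MTD rule is affected.

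**What to change.** - **Loperamide:** amend footnote v of Table 2 and footnote x of Tables 3 and 4 to the Section 6.7.4.1 dosing: 4 mg at first onset, then 2 mg every 2 hours, with a 2 mg first dose allowed only for recurrent, non-severe diarrhoea.
- **Dexamethasone:** amend footnote w of Tables 3 and 4 to the QD rule of Section 6.7.4.2: 4 mg with each AZD1775 dose unless contraindicated or not tolerated. If the sponsor instead wants a first-day minimum for QD patients, it should amend the QD paragraph of Section 6.7.4.2 and leave footnote w as it is. Either way, one rule should appear in both places.

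The cost is the wording of five footnotes, or of three footnotes and one paragraph under the alternative. No visit, procedure, patient or outcome definition changes.
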